#### 3.3.1.2 Pharmacovigilance Personnel

Designated safety management personnel (at Sponsor designated Pharmacovigilance vendor) have the capability to unblind individual subject treatment assignment in the case of determining the causality of potential suspected unexpected serious adverse reaction (SUSAR) events upon approval from the blinded Sponsor Medical Monitor who will confirm, based on blinded data review, whether the event is considered 'unexpected' for reporting purposes, and therefore a potential SUSAR. Unblinding for these circumstances is performed and recorded within the study randomization platform, i.e., the IRT system. Designated Sponsor personnel will review unblinded SUSARs that require submission to the regulatory agencies and/or central Institutional Review Boards (IRB). The Food and Drug Administration (FDA) submission vendor will receive unblinded MedWatch forms from the Pharmacovigilance vendor for submission of SUSARs to FDA.

#### 3.3.1.3 Investigator Unblinding in Case of Medical Emergency at the Site

The site investigator may exercise the option to unblind an individual subject in case of medical emergency. The unblinding by the investigator is performed, documented, and maintained within the context of the IRT system. Subject unblinding in these circumstances by the investigator and/or sponsor medical monitor will be documented by the site within the study medical records, the eCRF and described in the CSR.

#### 3.3.1.4 Biometrics

All biometrics personnel from sponsor and CRO (including Data management, Biostatistics and Statistical programming) will remain blinded during the study before database lock, unless otherwise specified.

#### a. Pharmacokinetic/Pharmacodynamic Data

Subject-level PK and exploratory PD endpoint data are unblinding. Therefore, the PK lab will not share the unblinded PK data with sponsor until after the database lock. The sample analysis for PD will not be performed until after database lock.

#### b. Randomization System/Process Personnel

The randomization vendor, whose function is to generate/confirm/upload the study randomization schedule and who support the day-to-day function of the IRT system (as per the

vendor established SOPs), will be unblinded. These unblinded personnel will not engage in study team meetings where any facets of the trial are being discussed.

Complete details of blinding/unblinding can be found in the Sponsor's Blinding and Unblinding Procedures Plan.

#### 3.4 Sample Size Justification

For the primary endpoint of percentage change from baseline in body weight, a sample size of 150 participants (stratified by gender and randomized 1:1:1 into three treatment arms) provides >95% power to detect a treatment difference of 4% weight reduction after 13 weeks of treatment with a 2-sided alpha of 0.05, assuming a standard deviation of 4% and 20% drop out.

#### 4 Analysis Sets

The following analysis set are defined and used for this study.

#### 4.1 Screened Set

The Screened Set includes all subjects who sign the informed consent form.

#### 4.2 Modified Intent-to-Treat (mITT) Analysis Set

The mITT analysis set consist of all randomized participants who receive at least one dose of the study drug during the double-blind treatment period. The participants will be analyzed as randomized. The mITT analysis set will be used for demographic, baseline characteristics and efficacy analyses.

#### 4.3 Safety Analysis Set

The Safety Analysis Set consist of all randomized participants who receive at least one dose of study drug during the double-blind treatment period. The safety analysis set will be used for safety analysis and analyzed as treated.

#### 4.4 Pharmacokinetic (PK) Analysis Set

The PK analysis set consist of all participants who receive study drug and have at least 1 measurable plasma concentration.

#### 4.5 Per Protocol Analysis Set

The per protocol analysis set consist of all participants who completed 13-week treatment and have weight assessment at week 13 and treatment compliance >=80%. Participants who completed treatment but have week 13 assessment done more than 3 days after last dose date and participants whose weights at week 13 are collect at non-fasted state are excluded.

#### 5 Statistical Methods

#### 5.1 General Considerations

Unless otherwise specified, all statistical analyses of the study will be performed using the statistical software Statistical Analysis System (SAS) for Windows Version 9.4 or later (SAS Institute, Inc., Cary, NC). All by-subject data used in the analyses will be displayed in listings.

#### 5.1.1 Data Summary

All summary tables will be presented by treatment group (K-757, K-757 + K-833, and placebo) and/or overall, as needed.

Unless otherwise specified, continuous variables will be summarized using descriptive statistics, the number of participants (n), mean, standard deviation (SD), minimum (min), first quartile (Q1), median, third quartile (Q3) and maximum (max). The min and max values will be presented to the same number of decimal places as the raw data. If the raw data has 3 decimal places or more, 3 decimal places will be presented for the mean and SD; 2 decimal places will be presented for medium, Q1, Q3, min and max. Otherwise the mean and median will be presented to one more decimal place than the raw data. The SD will be presented to two more decimal places than the raw data.

Summaries for categorical (discrete or dichotomous) variables will include the number and/or percentage of subjects in a particular category. Percentages will be presented to one decimal place, unless otherwise specified. Population counts (either number of subjects or number of time points at the assessment) for each treatment group will be used as the denominator in the calculation of percentages unless otherwise specified.

All tests of treatment effects will be conducted at a two-sided alpha level of 0.05 and/or two-sided 95% CI, unless otherwise stated.

#### 5.1.2 Baseline

Unless otherwise specified, baseline is defined as the last available observation prior to dosing during the double-blind treatment period.

Change from baseline is defined as the difference between the post-baseline assessment value and the baseline value, i.e.,

Post-baseline Assessment Value – Baseline Value.

Percent change from baseline is defined as

#### 5.1.3 Study Day

Study day is relative to the day of first dose of study drug. Day 1 is defined as the day of the first dose of study drug. Study day after Day 1 is calculated as:

Assessment date – date of Day 1 + 1.

Study day prior to Day 1 is calculated as:

Assessment date – date of Day 1.

The day prior to Day 1 is Day -1.

#### 5.1.4 Unscheduled Visits

An unscheduled visit value may be used to provide a measurement for a scheduled visit, a baseline, a last or a worst value, if appropriate according to their definitions. Unscheduled visits measurements may also be included in analyses for body weight, hemodynamic data (systolic blood pressure, diastolic blood pressure and heart rate) and lab measures (total cholesterol, LDL, HDL, and triglycerides). For lab data (safety lab and lipid panels), if an unscheduled visit occurs on the same date of a scheduled visit, it will be mapped to the scheduled visit. The duplicated lab values will be averaged for summary analysis. Other unscheduled visit values will not be summarized, but will be presented chronologically in the listings.

#### 5.1.5 Handling of Missing or Incomplete Data

For Efficacy endpoints, PK and PD, handling of missing data is described in Sections 5.7.2 and 5.10.

Unless otherwise specified, missing or incomplete dates for prior/concomitant medications, AEs and laboratory data will be imputed as follows:

#### **Adverse Events**

The following imputation rules for missing or partial AE start dates are used:

- If only Day is missing, the start day will be the first day of the month or the date of study drug first dose if the AE end date is on/after the date of study drug first dose or is missing/partial AND the start year and month of the AE are the same as year and month of the study drug first dose date;
- If Day and Month are both missing, the start date will be the date of study drug first dose if the AE end date is on/after the date of study drug first dose or is missing/partial AND the start year of the AE is the same as year of the study drug first dose date; the start date will be imputed to January 1 of the year otherwise.

• If Day, Month, and Year are all missing, the date will not be imputed. However, if the AE end date is on/after the date of study drug first dose, then the AE will be considered a treatment emergent adverse event (TEAE).

Missing or partial AE stop dates will not be imputed.

If the severity of an AE is missing, it will be classified as "severe" in the summary tables. If the assessment of relationship of study medication is missing, it will be classified as "related" to the study drug.

#### **Prior or Concomitant Medications**

The same imputation rule as applied to missing or partial AE start date will be used for missing or partial medication start dates.

Missing or partial medication stop dates will not be imputed.

#### **Safety Laboratory Data**

For the analysis/summary of laboratory data, lab values preceded by a "<" or a ">" sign (i.e., those below the lower limit of quantification [LLOQ] or above the upper limit of quantification [ULOQ]) will be considered equal to the LLOQ or ULOQ, respectively. The original values preceded by a "<" or a ">" sign will be presented in the listings.

#### 5.1.6 Analysis Visit Windows

For body weight, hemodynamic data (systolic blood pressure, diastolic blood pressure and heart rate) and lab measures (total cholesterol, LDL, HDL, and triglycerides), unscheduled visits and end of treatment visits and follow-up visits for participants who discontinued study drug earlier will be mapped based on analysis visit window below. The analysis visit windows will be exhaustive so that all available values obtained from unscheduled visits, end of treatment visits and follow-up visits for participants who discontinued study drug earlier have the potential to be summarized. No analysis visit windows will be applied for the study scheduled visits.

For other safety measures, analysis visit windowing will not be applied. The visits and time points reported on the electronic case report form (eCRF) will be used.

The following analysis visit windows will be used to map the unscheduled visits, end of treatment visits and follow-up visits for participants who discontinued study drug earlier of body weight.

Visit	Target Day	Analysis Visit Window Based on Study day
Baseline	1	1
Week 4	29	[2, 43]
Week 8	57	[44, 74]

Week 13 for Participants Discontinued Treatment	92	[75, 95]
Week 13 for Participants Completed Treatment	92	[75, Last Dose Date +3]
Week 15 for Participants Discontinued Treatment	105	>95

The following analysis visit windows will be used to map the unscheduled visits, end of treatment visits and follow-up visits for participants who discontinued study drug earlier hemodynamic data (systolic blood pressure, diastolic blood pressure and heart rate).

Visit	Target Day	Analysis Visit Window Based on Study day
Baseline	1	1
Week 1	8	[2,11]
Week 2	15	[12,18]
Week 3	22	[19,25]
Week 4	29	[26, 36]
Week 6	43	[37, 50]
Week 8	57	[51, 64]
Week 10	71	[65, 81]
Week 13 for Participants Discontinued Treatment	92	[82, 95]
Week 13 for Participants Completed Treatment	92	[82, Last Dose Date +3]
Week 15 for Participants Discontinued Treatment	105	>95

In the event of multiple measurements of the same test in the same window, if the measurements are from different visit categories, the priority order is scheduled visit, end of study visits and follow-up visits, then unscheduled visit. For the measurements in the same visit category, the value measured nearest to the target day will be used; if they are at the same distance to the target day, the latest one will be used.

#### 5.2 Subject Disposition

The number and percentage of participants who were randomized, who were randomized but did not receive the study drug as randomized, who were treated with the study drug, who completed the double-blind treatment and/or the study, who prematurely discontinued the study drug and/or study and the primary reason discontinuation (study drug and/or study) will be summarized by treatment group and overall.

A separate summary will be provided for the number and/or percentage of subjects that were screened, enrolled and screened failed (including initial screen and re-screen) and reason for screen failure.

Subject disposition will be listed for all randomized participants. Also, the eligibility status for the study will be listed for all screened participants, using the Screened Set.

#### 5.3 Protocol Deviations

Protocol deviations identified during the course of the study will be classified as major or minor.

A major protocol deviation (sometimes referred to as a protocol violation or a significant protocol deviation) is a deviation to the protocol that might significantly impact the completeness, accuracy or reliability of the study data or that may significantly affect a participant's rights, safety or well-being.

Before the database lock, all protocol deviations will be reviewed by the Sponsor. Final determination of major deviations is the responsibility of the Sponsor. Major protocol deviations will be identified and listed in the CSR.

Major protocol deviations will be summarized by treatment group and overall, and by category and sub-category if there is a sufficient number of major protocol deviations.

All protocol deviations will be presented in a listing. A by-subject listing will be provided for major protocol deviations.

#### 5.4 Demographics and Baseline Characteristics

Demographics and baseline characteristics will be summarized by treatment group and overall using the mITT set. Demographics and baseline characteristic include age, age group (< 65 years or  $\geq$  65 years), sex, childbearing potential if female, race, ethnicity, baseline height (cm), weight (kg) and body mass index (BMI; kg/m^2).

BMI, if not available, will be calculated as the ratio of subject's weight (kg) to the square of the subject's height (m):

$$BMI = Weight (kg)/(Height [m])^2$$
.

Continuous variables (age, height, weight and BMI) will be summarized by n, mean, SD, median, min, and max. Number of subjects and percentages will be used to describe categorical variables (sex, race, ethnicity and age group.).

Demographic and baseline characteristics data will be listed

#### 5.5 Medical History

Medical history will be coded using the latest version of Medical Dictionary for Regulatory Activities (MedDRA).

Medical history will be summarized by system organ class (SOC) and preferred term (PT) using the mITT set. A by-subject listing will be provided for medical history.

#### 5.6 Prior and Concomitant Therapies

#### **5.6.1** Prior and Concomitant Medications

Any medication or vaccine that the subject is receiving at the time of enrollment or receives during the study will be recorded in the subject's source documentation and the eCRF.

Medications will be classified into prior medications and concomitant medications.

- Prior medications are defined as medications that started and stopped prior to the first dose of study drug.
- Concomitant medications are defined as any medications that were ongoing or started on or after the first dose of study drug.

A given medication can be classified as a prior medication or a concomitant medication.

Medications will be recorded and coded using the latest version of World Health Organization (WHO) Drug Enhanced Dictionary. Prior and concomitant medications will be summarized separately by Anatomical Therapeutic Chemical (ATC) classification pharmacological or therapeutic subgroup (Level 2) and preferred drug name for the Safety Analysis Set. At each level of summarization, a subject is counted once if he/she reported 1 or more medications at that level. Medications will be listed by subject, including ATC classification, preferred drug name and reported drug name, the start and end dates (or ongoing status), dose, unit, frequency, route, and indication.

#### 5.6.2 Medications for Managing Gastrointestinal (GI) Adverse Events (AEs)

Medications for managing GI AEs is defined as any initiation and modification of medication taken on or after first dose to treat GI AEs. Number and proportion of participants with medication for GI AEs will be summarized by Anatomical Therapeutic Chemical (ATC) classification pharmacological or therapeutic subgroup (Level 2) and preferred drug name for the safety analysis set.

#### 5.7 Study Treatment Exposure and Compliance

#### 5.7.1 Exposure to Study Drug

Duration of exposure will be descriptively summarized by treatment group in the Safety Analysis Set.

Duration of exposure (days) will be calculated as:

Date of last dose - Date of first dose + 1.

#### 5.7.2 Treatment Compliance

Number and percent of participants with missing dose(s) and the total number of days with missing doses will be descriptively summarized by treatment group in the Safety Analysis Set.

Compliance will be calculated as follows:

Treatment compliance = Total number of days with complete dosing / Total number of actual dosing days \* 100

Participants are considered as taking complete dosing if full AM and full PM doses are taken. Treatment compliance will be summarized as a continuous variable with descriptive statistics by treatment group in the Safety Analysis Set. Treatment compliance will also be presented by the following specific ranges by treatment group: <50%,  $\ge50\%$  to  $\le80\%$ , >80% to <100% and 100%.

A by-subject listing will be presented for drug administration and compliance in the Safety Analysis set.

#### 5.8 Efficacy Analyses

All efficacy analyses will be performed using the mITT Set unless otherwise specified.

#### 5.8.1 Primary Efficacy Endpoint

The primary efficacy outcome is the % weight change from baseline (Week 0) to Week 13.

Per the protocol, weight will be taken in duplicate throughout the study, therefore, all analyses and summaries of weight will be based on the average of the duplicate weight measurements.

#### 5.8.1.1 Primary Estimand

**Primary trial objective**: To assess relative (%) change from baseline in body weight after 13 weeks of treatment with K-757 alone and in combination with K-833, in comparison to placebo

**Estimand Scientific Question of Interest**: What is the effect on body weight of assigning participants to K-757 alone and in combination with K-833, in comparison to placebo on treatment?

- Variable: % change in body weight
- Analysis Set: Modified intent-to-treat set
- Analysis time point: 13 weeks post-baseline
- Treatment: Average treatment effect of K-757 alone and in combination with K-833 relative to placebo
- Analysis methodology: Mixed model for repeated measures (MMRM)

- Intercurrent events: Treatment discontinuation All available data at Week 13 had participants remained on their randomized treatment for the entire planned duration of the trial are used in the analysis ("hypothetical" estimand).
- Missing data: Missing data is imputed using MMRM based on missing at random (MAR) assumption at Week 13.

#### 5.8.1.2 Primary Analysis

A mixed model for repeated measurements (MMRM) analysis will be applied with gender, treatment, visit and treatment-by-visit interaction as fixed effect, and baseline body weight as a covariate. The MMRM model will use assessments only from participants who are taking the randomized treatment until end of treatment if they complete treatment or until 3 days after discontinuation of randomized treatment; scheduled follow up assessment will also be included in analysis. An unstructured covariance will be used. If the unstructured covariance structure leads to nonconvergence, other covariance structures, such as, compound symmetry (CS) and autoregressive (AR(1)) will be used. Akaike's information criteria will be used to select the best covariance structure.

The least squares (LS) means, difference in LS mean (K757 vs placebo, K-757+K-833 vs placebo), the corresponding 95% CI and the p-value will be provided. In addition, descriptive statistics including number of participants, mean and standard error will be provided.

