## 5.5. Rationale for Study Population

The trial population will consist of individuals who are obese (BMI 30.0 to 40.0 kg/m^2, inclusive) These participants represent a clinically relevant population for pharmacotherapeutic weight management as they are at significant risk for weight related morbidities (such as hypertension, dyslipidemia, obstructive sleep apnea) and mortality and are likely to benefit from weight reduction. People with known cardiovascular disease (CVD) are excluded given the early stage of development and limited characterization of the safety profiles of the study regimens. A BMI > 40.0kg/m^2 is exclusionary to limit potential for occult CVD or other health issues that might increase the risk of participating in an early-stage clinical trial. People with T2DM are excluded due to the well-described confounding effect that improved glycemic control has on response to weight-loss interventions.

As first line treatment in weight management is lifestyle modification through a reduced-calorie diet and increased physical activity, only people who have tried but failed to attain weight loss goals with lifestyle modification will be eligible for participation.

Sex is an important response covariate with females typically achieving greater weight loss than males in obesity trials. Randomization will be stratified by sex to minimize potential bias. Weight loss trials have historically enrolled substantially more female than male participants. To ensure meaningful representation of both sexes, neither strata will be permitted to exceed 70% of total enrollment. Females of childbearing potential (FOCBP) are eligible for participation. Given the early stage of development and current lack of definitive embryo-fetal toxicology data for either K-757 or K-833, FOCBP must be using highly effective contraception with low user-dependence and undergo pregnancy testing at screening and specified timepoints during study participation.

Given the priority of avoiding spurious liver toxicity signals, excessive alcohol consumption, known history of liver disease (other than non-alcoholic fatty liver disease [NAFLD]), and excessive elevations in ALT, AST, and/or bilirubin at screening are exclusionary as specified in Section 8.2.

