### Mandatory fasted visits:

Amongst the in-person clinic visits during the Treatment Period, V2 (randomization), V6 (Day 29), V9 (Day 57) and V12 (Day 92), subjects should come to the clinic in the fasted state because body weight and fasting lipids need to be assessed in the fasted state. These fasted visits should be scheduled in the morning and the AM dose of study medication should be taken after collection of blood. Dosing should be witnessed at these visits. Other in-person visits during the Treatment Period can be in the fasted or fed state and may be scheduled without regard to timing of study medication.

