#### **Primary Estimand**

For the primary endpoints, the primary estimand for the percentage change from baseline in body weight is defined as the average treatment effect of K-757 alone and the combination of K-757 + K-833 relative to placebo in the mITT analysis population, had they remained on their randomized treatment for the entire planned duration of the trial (“hypothetical” estimand).

A mixed model for repeated measurements (MMRM) analysis will be applied with gender, treatment, visit and treatment-by-visit interaction as fixed effect and baseline body weight as a covariate. The MMRM model will use assessments only from participants who are taking the randomized treatment until end of treatment or until first discontinuation of randomized treatment. An unstructured covariance will be used. If the unstructured covariance structure leads to nonconvergence, Akaike’s information criteria will be used to select the best covariance structure.

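### The primary MMRM gives gender and baseline weight one coefficient for all visits; if their effects grow with time, gender is under-adjusted at Week 13 and the reported CI is slightly too wide (minor)

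*SAP*

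**What the plan says.** The protocol (16.6.1, Primary Estimand) specifies an MMRM with "gender, treatment, visit and treatment-by-visit interaction as fixed effect and baseline body weight as a covariate". SAP 5.8.1.2 repeats these terms ("with gender, treatment, visit and treatment-by-visit interaction as fixed effect, and baseline body weight as a covariate") and adds: "An unstructured covariance will be used". No section of either document adds a covariate-by-visit term.

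Body weight on treatment is taken at randomization and at Weeks 4, 8 and 13 (protocol 9.2, mandatory fasted visits). SAP 5.8.1.2 also says that "scheduled follow up assessment will also be included in analysis", so Week 15 may be a fourth visit in the model.

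Randomization is stratified by gender, and neither gender may exceed 70% of enrolment (protocol 7.1). Protocol 5.5 gives the reason: "Sex is an important response covariate with females typically achieving greater weight loss than males in obesity trials". It states a direction, but no size and no time course.

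The same MMRM serves the kg change (SAP 5.8.2.2), the imputation behind the 5% responder endpoint (SAP 5.8.2.1) and the treatment-policy estimand (protocol 16.6.1, SAP 5.8.1.3).

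**The concern.** Percent change from baseline is zero for everyone at Day 1. If women end up losing more than men, the gap has to open after that, and it is natural to expect it to be larger at Week 13 than at Week 4. A model with one gender coefficient cannot follow such a gap. It fits a compromise, and under unstructured covariance the compromise sits close to the precise early visits. The stratification factor would then be least well adjusted for at the primary time point.

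Two things could follow. The gender variation left in the Week 13 residual would inflate the reported SE. And if discontinuation changes the gender mix differently in the active and placebo arms, the unfitted part of the gap would enter the treatment contrast. The same reasoning applies to baseline weight if its effect on percent change also grows.

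**Working it through.** **1. The plan's own power.** SAP 3.4 states "power to detect a treatment difference of 4% weight reduction after 13 weeks of treatment with a 2-sided alpha of 0.05" and puts that figure above 95%. It takes an SD of 4 points and a dropout of 20%. With 50 × 0.8 = 40 evaluable per arm, SE = 4 × √(2/40) = 0.894 and 4/0.894 = 4.472. Power = Φ(4.472 − 1.960) = 99.4% (99.3% with the noncentral t). The claim reproduces.

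**2. Inputs for the check.** From the documents: Week 13 SD 4, effect 4 points, 50 per arm, 20% dropout, at most 70% of one gender. Assumed: SDs of 1.8 and 2.8 at Weeks 4 and 8; correlations 0.85 (Weeks 4 and 8), 0.70 (4 and 13) and 0.88 (8 and 13); the size and shape of the gender gap; any split of dropout by gender or arm. Three visits are used throughout; Week 15 is left out.

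**3. What the single gender coefficient estimates.** With complete data it is a weighted mean of the visit-specific gaps, with weights w = V⁻¹1 / (1′V⁻¹1), where V is the covariance matrix across visits. The inputs above give weights of 1.38, −0.32 and −0.07 on Weeks 4, 8 and 13. For a gap proportional to time that reaches G at Week 13, the fitted gap is (1.382 × 4/13 − 0.316 × 8/13 − 0.066) × G = 0.16G, so about 0.84G is left unadjusted at Week 13. With no correlation at all the weights would be 0.62, 0.26 and 0.13 and the fitted gap 0.47G, so under-adjustment does not depend on the negative weights.

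**4. Effect on the reported SE.** The unfitted gap adds p(1 − p) × (unfitted gap)² to the Week 13 variance of 16. With p = 0.70 women, p(1 − p) = 0.21:

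| G (points) | Fitted | Unfitted | Added variance | SE ratio |
|---|---|---|---|---|
| 1 | 0.16 | 0.84 | 0.15 | √(16.15/16) = 1.005 |
| 2 | 0.33 | 1.67 | 0.59 | √(16.59/16) = 1.018 |
| 3 | 0.49 | 2.51 | 1.32 | √(17.32/16) = 1.040 |

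Large-sample MMRM fits with dropout agree: 0.4% to about 4%. The shape of the gap matters. A late-opening gap of 0.5/1.5/3.0 points with 65% women gives √((16 + 0.2275 × 2.98²)/16) = 1.061 from gender alone.

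A second set of simulations used 65% women and 20% dropout in all arms, and let the baseline-weight effect grow as well. The model-based SE at 50 per arm was 0.857 under the plan against 0.850 with interactions (gap 0.3/0.6/1.0), 0.891 against 0.855 (0.5/1.2/2.0) and 0.942 against 0.852 (0.5/1.5/3.0), that is 1%, 4% and 11% larger.

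**5. Effect on actual variability.** In 400 simulated trials of 50 per arm with equal 20% dropout, the empirical SEs in those three settings were 0.854 (plan) against 0.856 (interactions), 0.935 against 0.929, and 0.868 against 0.870. Each carries Monte Carlo error of about 0.87/√800 = 0.03, but both models were fitted to the same data sets. When the gender mix is similar across arms, the unfitted gap largely cancels in the contrast. The reported SE overstates the uncertainty a little; the estimate itself is about as precise.

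**6. Bias.**
- Dropout differing by gender but alike in all arms (men 10%, women 25%; or men 0%, women 40%): the two models agree within about 0.01 point.
- Placebo 20%, active 30% in women and 8% in men, 70% women: women are 0.49/(0.49 + 0.276) = 64% of active completers against 70% on placebo. With G = 2, a crude figure that ignores earlier visits is 0.06 × 1.67 = 0.10 points. The MMRM recovers part of this through the earlier weights. Two sets of large-sample fits with gaps of 1 to 3 points gave 0.03 to 0.10 and 0.02 to 0.07 points toward zero.
- Placebo 20%, active 25% in women and 10% in men, 65% women: 0.03, 0.06 and 0.09 points toward zero for the three gap patterns in step 4.
- Deliberately extreme splits (for example 50% dropout in active women and 10% in everyone else) gave 0.09 to 0.31 points, and a fully crossed pattern up to 0.41.

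**7. Power again.** Taking the worst SE inflation and a 0.10-point bias together: SE = 0.894 × 1.11 = 0.993, 3.9/0.993 = 3.93, and Φ(3.93 − 1.96) = 97.5%. Simulated power under the planned model was at least 98.3% in every scenario run at 50 per arm.

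**The case against.** The case for leaving the model alone is fair in several respects. Protocol and SAP agree on the terms, so there is no contradiction to resolve. Growth of the gender effect is an inference from the endpoint; protocol 5.5 gives only a direction. The support is weaker for baseline weight, since nothing in the documents says that it predicts a percent change already scaled to baseline. SAP 3.4 does not split the 20% dropout by gender or arm, so every bias figure rests on an invented pattern. All of this stands, and it keeps the severity low.

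Two stronger readings are tempting and should not be drawn. A reader might infer that any difference in dropout between men and women biases the Week 13 contrast. It does not: under gender-stratified randomization such a pattern affects all arms alike and cancels. A reader might also infer that the trial loses real precision or that its power is at risk. Steps 5 and 7 show neither.

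The subgroup analyses by gender (SAP 5.8.3) fit men and women separately and so share no gender coefficient, but they do not repair the primary contrast.

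**Conclusion.** A minor point that holds conditionally. The constraint itself is plain in the text. Its consequences depend on effects that grow with time, which is plausible for cumulative weight loss but is an assumption.

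Under that assumption the Week 13 SE and CI are reported about 0.4% to 4% too wide for gender gaps of 1 to 3 points proportional to time, and up to about 11% with a late-opening 3-point gap and a growing baseline-weight effect. Bias needs a gender pattern of dropout that differs between arms. Under the moderate patterns assumed it is about 0.02 to 0.10 points, at most 0.10/0.87 = 11% of one SE. It runs toward zero because those patterns have women leaving active treatment more often; the reverse pattern, which was not simulated, would be expected to reverse the sign. The claim of more than 95% power is unaffected.

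**What to change.** Add gender-by-visit and baseline-weight-by-visit interactions to the MMRM in SAP 5.8.1.2 and protocol 16.6.1. Carry the same terms into the kg-change model, the imputation model for the 5% responder endpoint and the treatment-policy model. Make the change before database lock so that it remains prespecified. If only the SAP is revised, record the departure in SAP Section 8, which now states that there are none.

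The cost is wording plus two extra parameters per covariate with three visits (Weeks 4, 8 and 13), or three if the Week 15 follow-up stays in the model. With about 150 participants that is negligible, and almost nothing is lost if the effects turn out to be constant over time.
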